### **Main Outcome Measures**

The primary outcome measure was the mean change in corneal surface staining (guided by use of fluorescein and lissamine green) at weeks 1, 2, 4, 8 and 12 based on the NEI grading scale. Corneal fluorescein staining was graded from 0 to 3 (none to heavy) in five regions of the cornea and summed for a total score.

All secondary outcome measures followed the same timeline with comparison at weeks 1, 2, 4, 8 and 12 in comparison to baseline. Secondary outcome measures included the mean change in tear break-up time (TBUT), the mean change in conjunctival staining (graded 0-3 in 6 regions), the mean change in tear osmolarity as measured by TearLab, the mean change in DEQ-5, the mean change in meibomian gland scores as measured by quality of meibum expression, the mean change in best-corrected distance visual acuity (BCDVA) as measured by ETDRS chart and the mean change in Schirmer's score as measured by a Schirmer's test strip.

Meibomian gland scoring involved grading the quality of expression (0-3) from 15 glands along the lower eyelid including temporal, central and nasal. For scoring, 3 was representative of clear, liquid secretions and 0 was no secretions. The DEQ-5 Dry Eye Questionnaire was used to evaluate symptoms and characterize severity of discomfort, dryness and tearing. Possible scores ranged from 0 to 22 with higher scores representing worse symptoms.

On the screening visit and the initiation of therapy including implantation of the dexamethasone insert in the study group, a physician ease of insertion questionnaire was also completed by the physician implanting the device. All device-related complications were recorded. All subject-reported adverse events were recorded at each study visit.

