2. STUDY OBJECTIVES

2.1. Primary Objective

- Mean change in ocular surface staining (sodium fluorescein and lissamine green) from baseline at week 1, week 2, week 4, week 8 and week 12 as measured by the NEI grading scale

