I. The investigator will use the NEI scale to grade the cornea using fluorescein and the conjunctiva using lissamine green at visits 1, 2, 3, 4, 5, 6.

II. The investigator will grade the level of ocular injection on a 0 to 4-point scale at visits 1, 2, 3, 4, 5, 6.

0 = None

1 = Mild – Slightly dilated blood vessels; color of vessels is typically pink; can be quadrantal

2 = Moderate – More apparent dilation of blood vessels; vessel color is more intense (redder); involves the majority of the vessel bed

3 = Severe – Numerous and obvious dilated blood vessels; in the absence of chemosis the color is deep red, may be less red or pink in presence of chemosis, is not quadrantic

4 = Extremely Severe – Large, numerous, dilated blood vessels characterized by unusually severe deep red color, regardless of grade of chemosis, which involves the entire vessel bed

III. The investigator will evaluate the expressibility and quality of the meibomian glands at visits 1, 2, 3, 4, 5, 6..

Grade scale for meibomian gland dysfunction		
Grade Scale	Percentage of blocked glands	Quality of meibomian secretion
Grade 1	40% - 50%	Clear to mild milky secretion
Grade 2	50% - 70%	Milky to pasty secretion
Grade 3	70% - 85%	Thick, pasty to very little secretion
Grade 4	85% - 90%	Very little to no secretion

IV. The investigator will use the InflammaDry to detect levels of MMP9 at visits 1, 2, 3, 4, 5, 6.

[figure not shown]

InflammaDry

[name] STUDY V1

V. The investigator will use Tear Lab to assess tear osmolarity at visits 1,2, 3, 4, 5, 6.

VI. The investigator will fill out the following questionnaire on the day of DEXTENZA® insertion (Screening visit):

Physician Ease of Insertion Questionnaire

The investigator will grade the level of ease of insertion of the intracanalicular insert on a 0 to 10-point scale.

The Investigator will record ease of insertion procedure on the appropriate Case Report Form.

0	1	2	3	4	5	6	7	8	9	10
---	---	---	---	---	---	---	---	---	---	----

Very Easy

Very Hard

VII. The investigator will have the patient complete the DEQ-5 questionnaire at visits 1,3,4,5,6,7.

DEQ-5

1. Questions about EYES DRYNESS:

a. During a typical day in the past month, how often did your eyes feel discomfort?

Never
 Rarely
 Sometimes
 Frequently
 Constantly

b. When your eyes feel discomfort, how intense was this feeling of discomfort at the end of the day, within two hours of going to bed?

Never have it Not at all intense Very intense

0
 1
 2
 3
 4
 5

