## Patients

60 eyes of 30 patients age  $\geq 18$  with clinically diagnosed aqueous-deficient dry eye disease and determined to be a candidate (based on clinical judgment) for treatment with a topical immunomodulator were enrolled in the study.

Patients were excluded if they had been on topical immunomodulation therapy in the 3 months prior to screening, were actively being treated with topical, oral or intravenous immunosuppressive agents, had a hypersensitivity to dexamethasone, had active infectious systemic or ocular disease or had altered nasolacrimal flow of either acquired or congenital origin. Pregnant patients were also excluded.

Following screening and informed consent, patients were randomized into 3 groups; a study group and 2 control groups. Each group included 10 patients. The study group was started on cyclosporine 0.05% and was implanted with an intracanalicular, 0.4 mg dexamethasone insert in both eyes. The first control group was started on cyclosporine 0.05% in conjunction with topical loteprednol 0.5% twice daily. The 2nd control group was started on cyclosporine 0.05% as monotherapy.

The study period lasted 12 weeks including one screening/prescription visit and follow-up visits which occurred at weeks 1, 2, 4, 8 and 12 following initiation of therapy. At weeks 1, 2, 4, 8 and 12 the primary and secondary endpoints were assessed.

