## **RESULTS**

### **Patient Demographics**

Sixty eyes of 30 subjects were successfully enrolled into the study including 20 eyes of 10 subjects in the dexamethasone/cyclosporine group, 22 eyes of 11 subjects in the loteprednol/cyclosporine group and 18 eyes of 9 subjects in the cyclosporine monotherapy group. All 3 groups were summarized by baseline characteristics, which are shown in Table 2.

None of the three groups, including the study and two control groups met the primary endpoint. In the dextenza group, the mean baseline corneal staining score was  $0.5 \pm 1.0$  with 70% ( $n=14$ ) without evidence of corneal staining at baseline. The mean score at weeks 4, 8 and 12 was  $0.6 \pm 1.0$  ( $P = 0.99$ ),  $0.5 \pm 1.1$  ( $P = 0.99$ ) and  $0.7 \pm 1.4$  ( $P = 0.97$ ), respectively. In the loteprednol group, the mean baseline corneal staining score was  $0.8 \pm 1.5$  with 64% ( $n=14$ ) without corneal staining at baseline. At weeks 4, 8 and 12, the mean score was  $0.9 \pm 0.9$  ( $P = 0.99$ ),  $0.0 \pm 0.0$  ( $P = 0.06$ ) and  $0.6 \pm 1.0$  ( $P = 0.78$ ), respectively. In the cyclosporine monotherapy group, the mean baseline corneal staining score was  $0.5 \pm 0.5$  with 50% ( $n=9$ ) of eyes absent of any corneal staining at baseline. There was no significant change in corneal staining at any time point with a mean score of  $1.1 \pm 1.4$  ( $P = 0.26$ ),  $0.3 \pm 0.6$  ( $P = 0.63$ ) and  $0.5 \pm 0.7$  ( $P = 0.99$ ) at weeks 4, 8 and 12, respectively. These results, in addition to comparisons of other outcome measures, are summarized in Table 3.

There was no significant change in conjunctival staining, Schirmer scores, TBUT, tear osmolarity or meibomian gland scores at any of the follow-up time points in comparison to baseline in all three groups. These results are summarized and also demonstrated in Table 3.

Across all visits, the mean IOP remained stable in all three groups. In the cyclosporine monotherapy group, there were no instances of IOP elevation  $>10$  mmHg above baseline. Similarly, in the dextenza and loteprednol groups, there were no instances of IOP elevation  $>10$

mmHg above baseline at any time point. There were no canalicular-related complications or adverse events related to implantation of the dexamethasone insert. No patients required removal of the insert.

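### The SAP makes only the corneal half of the protocol's staining endpoint primary, unlabelled in the supplied text, and prints no staining means for weeks 1 and 2

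*SAP*

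**What the plan says.** **Protocol.** Section 2.1 sets the primary as "Mean change in ocular surface staining (sodium fluorescein and lissamine green) from baseline at week 1, week 2, week 4", and continues to weeks 8 and 12 on the NEI grading scale. The synopsis says the same. Appendix I says what each dye is for: the investigator will "grade the cornea using fluorescein and the conjunctiva using lissamine green" at all six visits. The protocol does not say whether the two scores are summed or judged separately.

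**SAP, Main Outcome Measures.** The primary is introduced with "The primary outcome measure was the mean change in corneal surface staining (guided by use of fluorescein and lissamine green". The only score then described for it is corneal: "Corneal fluorescein staining was graded from 0 to 3 (none to heavy) in five regions of the cornea and summed for a total score". The list of secondary outcomes includes "the mean change in conjunctival staining (graded 0-3 in 6 regions".

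**SAP, Patients.** "At weeks 1, 2, 4, 8 and 12 the primary and secondary endpoints were assessed".

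**SAP, Statistical Analysis.** Repeated measures analysis of variance within each group is followed by Bonferroni-corrected comparisons of each time point with baseline. The number of comparisons is not given.

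**SAP, Results.** "None of the three groups, including the study and two control groups met the primary endpoint". Corneal means and P values follow for weeks 4, 8 and 12. For the conjunctiva and other measures, in all three groups, "There was no significant change in conjunctival staining, Schirmer scores, TBUT, tear osmolarity or meibomian gland scores at any of the follow-up time points". The results table (printed as Table 2) shows baseline and months 1, 2 and 3 only.

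**The concern.** Both dyes are named in the SAP's primary, so it reads at first like the protocol's. But the protocol uses lissamine green to grade the conjunctiva, and the SAP puts the conjunctival score among the secondaries. A reader of the supplied SAP text cannot tell that the primary was narrowed, when, or why.

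The missing visits add to this. The SAP describes the insert as releasing drug over 30 days, and the protocol prescribes Lotemax for one month. Weeks 1 and 2 are therefore two of the three visits that fall within about a month of steroid exposure. The SAP introduction gives faster response as a reason for adding a steroid, so these are the visits where an early effect would be looked for.

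At stake is what the not-met verdict covers: which component, which visits, and how many tests were corrected for.

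**Working it through.** **1. Share of the protocol's staining assessment kept as primary.** On the SAP's own scales the cornea is 5 regions x 3 = 15 points and the conjunctiva 6 regions x 3 = 18 points. The SAP's primary covers 15 of 15 + 18 = 33 points (45%). The other 18 are secondary.

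**2. Printed against planned means.**

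- Planned: 2 components x 5 visits x 3 groups = 30 post-baseline means.
- Printed: 2 x 3 visits x 3 = 18.
- Absent: 30 - 18 = 12 (40%), all at weeks 1 and 2.

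**3. What the Results text says about weeks 1 and 2.**

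| Component | Group | Coverage of weeks 1 and 2 |
|---|---|---|
| Conjunctiva | all three | in words: no significant change at any follow-up |
| Cornea | monotherapy | in words: no significant change at any time point |
| Cornea | insert, loteprednol | only the overall not-met statement |

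**4. Can the printed P values show how many comparisons were used?** The usable figure is the loteprednol cornea at week 8. Inputs from SAP Results and Table 2: baseline 0.8 ± 1.5, week 8 0.0 ± 0.0, 22 eyes, reported P = 0.06. Because the week 8 SD is zero, each eye's change is minus its baseline, so the SD of the change is 1.5. I assume that all 22 eyes were seen at week 8, that the eye is the unit, and that the test is two-sided.

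- t = 0.8 / (1.5/√22) = 2.50.
- Separate paired t test, df 21: P = 0.0207. Times 3 = 0.062; times 5 = 0.104. Here three comparisons reproduce the reported 0.06.
- Pooled error term from the repeated measures analysis, complete data: df = 21 x 5 = 105 for five follow-ups or 21 x 3 = 63 for three. At the same t, times 5 = 0.070 and times 3 = 0.045, so 0.06 lies between them. The pooled SD is not printed. If it were 1.47, t = 0.8 / (1.47/√22) = 2.55 and times 5 is about 0.06.
- Whole-number check. With 14 unstained eyes, 8 stained eyes, and a mean and SD that round to 0.8 and 1.5, exactly 9 sets of scores are possible. Across them the separate test times 3 runs from 0.049 to 0.077. The pooled test times 5 (df 105, using each set's own SD) runs from 0.051 to 0.091. Both ranges include 0.06.

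The reported value fits three comparisons under one reading of the method and five under another. It cannot settle the count.

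**5. Does the verdict change if the conjunctiva is restored?** If the components are judged separately, the cornea is reported as not met, and the conjunctiva is reported with no significant change in any group at any follow-up. On the reported results, neither component succeeds. A summed score cannot be tested from the printed summaries, because the correlation between the two components is not given, and the protocol does not define such a score.

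**The case against.** The strongest reply is that nothing of substance turns on this. Conjunctival staining was reclassified and reported, not dropped, and its result is null. The SAP discussion calls efficacy unclear and names the small samples and the lack of a staining entry criterion as limitations. Text that would label the change could also sit in the SAP pages that were not supplied. All of this stands. It limits the point to coverage and transparency, and limits the labelling criticism to the supplied text.

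A reader might infer from P = 0.06 that weeks 1 and 2 were left out of the correction. The documents do not support that: the SAP names a repeated measures analysis, and with a pooled error term five comparisons fit as well. For the same reason one cannot say that a five-visit correction would raise that P value; if five were already used, nothing moves.

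A reader might also infer that restoring the protocol's primary would turn the trial positive. The reported conjunctival results point the other way.

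The reply does not answer the central mismatch. The two documents define different primaries, and the SAP says five visits were assessed but prints three.

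**Conclusion.** The point holds as a protocol–SAP inconsistency with incomplete reporting, and it should be fixed. The SAP's primary is one of the two protocol components, 12 of 30 planned staining means are not printed, and the size of the Bonferroni family is not stated. For the cornea in the two steroid groups, weeks 1 and 2 are covered only by the overall verdict.

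The verdict itself probably stands. That rests on judging the components separately and on accepting the SAP's statement about the conjunctiva, which comes without P values. It is probable rather than certain because the week 1 and 2 corneal results in the steroid groups cannot be checked, and because neither document, as supplied, gives a success rule.

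The absence from the results of MMP-9, conjunctival injection and visual acuity, and the insert group's baseline corneal score (0.5 in the text, 0.6 in the table), are separate minor reporting points.

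**What to change.** - **Main Outcome Measures.** Restore the protocol's primary as two separately reported components, corneal fluorescein in five regions and conjunctival lissamine green in six, at weeks 1, 2, 4, 8 and 12. Alternatively, keep the cornea-only primary and label it a deviation from the protocol, with its date and reason. Label any summed score as newly defined.
- **Results and results table.** Report and test both components at all five visits. If week 1 and 2 data were not collected, say so and correct the statement under Patients.
- **Statistical Analysis.** State the number of comparisons in the Bonferroni correction and make it match the visits tested.
- **Verdict.** Reword it to name both components and the visits covered.

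The cost is some rewording and a little more analysis. If the week 1 and 2 data exist, as the SAP says, no new collection is needed. The correction may become stricter if fewer visits were counted before.

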Intracanalicular Dexamethasone used in conjunction with Restasis (cyclosporine ophthalmic emulsion) for the treatment of signs and symptoms of dry eye disease as compared to Restasis with Lotemax (loteprednol etabonate ophthalmic suspension 0.5%) and Restasis monotherapy.

[name] STUDY

Compound:

DEXTENZA® (dexamethasone ophthalmic insert) 0.4 mg for intracanalicular use

Study Name:

[name] STUDY

Protocol Number:

TC-2020-DexRes

Clinical Phase:

Open label prospective

Date of Issue:

01/11/2021

Primary Investigator:

[name]

Site Name & Location:

Cleveland Eye Clinic
[name],
[name]

[name] STUDY V2

CLINICAL STUDY PROTOCOL SYNOPSIS

TITLE	Intracanalicular Dexamethasone used in conjunction with Restasis (cyclosporine ophthalmic emulsion) for the treatment of signs and symptoms of dry eye disease as compared to Restasis with Lotemax (loteprednol etabonate ophthalmic suspension 0.5%) and Restasis monotherapy.
SITE LOCATION(S)	Cleveland Eye Clinic [name]
PRINCIPAL INVESTIGATOR	[name]
OBJECTIVE(S)	To evaluate the benefit of treatment with a physician administered intracanalicular dexamethasone insert in patients with dry eye who are beginning treatment with Restasis (cyclosporine ophthalmic emulsion) to reduce the signs and symptoms of dry eye disease.
STUDY DESIGN	Prospective Open-label Interventional Study
STUDY DURATION	6 months including screening and enrollment
ESTIMATED STUDY COMPLETION DATE	3 months after date of insertion
POPULATION	
Sample Size:	30 patients (60 eyes)
Target Population:	Patients with dry eye who are about to begin treatment with Restasis bilaterally to reduce the signs and symptoms of dry eye disease and who have not been on topical immunomodulation for a minimum of 3 months prior to the start of the study.
TREATMENT(S)	

[name] STUDY V2

Study Drug	Sustained Release Dexamethasone, 0.4 mg
Dose/Route/Schedule:	All patients will be prescribed Restasis BID for both eyes who have not been on topical immunomodulation for a minimum of 3 months, and who would benefit from addition of topical pharmacotherapy (immunomodulation). There will be 3 groups. 10 patients will receive Restasis BID and Dextenza in both eyes, 10 patients will receive Restasis BID for 12 weeks and Lotemax BID for one month in both eyes and 10 patients will receive Restasis BID monotherapy.

Screening/ Prescription

- 1-week
- 2-week
- 1 month
- 2 month
- 3 month

ENDPOINT(s)

PRIMARY:

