### **Statistical Analysis**

All statistical analysis was performed using Prism 9 software (GraphPad Software, Inc.). Repeated measures analysis of variance was performed to compare the values at each time point in each group. Post hoc analyses were also performed with Bonferroni correction to directly compare the mean values at each time point in comparison to baseline. A *P* value less than 0.05 was considered statistically significant.

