Prior studies have demonstrated the favorable use of topical corticosteroids as an induction agent in combination with topical cyclosporine to augment the anti-inflammatory properties offered by cyclosporine. Although both the topical steroid and intracanalicular dexamethasone groups in this present study offered similar results, there are considerations unique to corticosteroids as it relates to sustained drug delivery. The sustained-release insert described herein offers theoretical benefits to bypass the challenges and potential side effects of topical corticosteroids. Topical agents, which are instilled intermittently, inevitably lead to variability in drug concentration owing to the poor bioavailability of the agent. The insert's intracanalicular location, with close proximity to the ocular surface, purports to offer a superior bioavailability profile with improved consistency of drug concentration in contrast to topical administration. The tapered delivery of drug from the insert over the course of 30 days minimizes the risk for rebound inflammation, which can occur with abrupt discontinuation of topical steroids. In addition, the preservative-free composition of the insert overcomes concerns related to preservatives and ocular surface toxicity, an established issue related to long-term use of topical drops.

This study has a number of limitations. The sample size was small in each group. The primary endpoint, which was improvement in corneal staining, was not met by any of the three groups. However, it is important to note that corneal staining was not a component of the inclusion criteria and thus future studies with refined inclusion criteria would be beneficial to evaluate the value of dexamethasone combined with cyclosporine 0.05% in improving corneal staining. Further, it's possible that an increase in sample size and an adequately powered study could lead to meaningful changes in other parameters such as TBUT and Schirmer scores, both of which have been demonstrated to improve following use of cyclosporine 0.05% in prior studies.

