## CONCLUSION

The challenges of topical medication use are widespread and well recognized across ophthalmology. The safety profile reported in this study, albeit a small sample size, indicates the dexamethasone intracanalicular insert is a safe alternative option to topical steroids to augment the anti-inflammatory properties of topical cyclosporine 0.05%. Further study is necessary but use of the dexamethasone insert may provide a means to optimize medication delivery without compromising safety or efficacy in the treatment of dry eye disease.

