**Table 2 - Results**

Parameter	Dextenza + Cyclosporine	Loteprednol + Cyclosporine	Cyclosporine monotherapy
Corneal staining			
• Baseline	0.6 ± 1.0	0.8 ± 1.5	0.5 ± 0.5
• 1 month	0.6 ± 1.0	0.9 ± 0.9	1.1 ± 1.4
• 2 month	0.5 ± 1.1	0.0 ± 0.0	0.3 ± 0.6
• 3 month	0.7 ± 1.4	0.6 ± 1.0	0.5 ± 0.7
Conjunctival staining			
• Baseline	0.5 ± 1.8	1.5 ± 1.8	0.4 ± 0.6
• 1 month	0.3 ± 0.6	0.9 ± 1.4	0.5 ± 0.7
• 2 month	0.4 ± 0.8	0.8 ± 1.8	0.3 ± 0.6
• 3 month	0.8 ± 1.7	1.0 ± 1.6	0.7 ± 1.4
Schirmer scores (mm/5 min)			
• Baseline	14.9 ± 10.3	10.3 ± 7.2	11.6 ± 10.5
• 1 month	15.4 ± 10.1	12.9 ± 9.1	10.1 ± 8.5
• 2 month	15.8 ± 9.4	12.4 ± 8.4	10.8 ± 6.4
• 3 month	12.3 ± 7.1	10.1 ± 6.0	9.6 ± 5.5
Tear breakup time (seconds)			
• Baseline	6.6 ± 2.2	5.4 ± 1.5	5.7 ± 3.3
• 1 month	8.0 ± 3.6	6.1 ± 2.8	7.4 ± 3.7
• 2 month	7.7 ± 3.1	6.2 ± 2.2	7.1 ± 3.4
• 3 month	7.7 ± 2.5	6.1 ± 2.4	7.3 ± 3.6
Tear osmolarity			
• Baseline	295.5 ± 17.4	311.3 ± 19.8	306.9 ± 28.4
• 1 month	304.4 ± 30.1	307.7 ± 17.3	307.9 ± 24.2
• 2 month	303.9 ± 22.1	300.1 ± 19.2	295.3 ± 20.7
• 3 month	299.5 ± 16.2	304.4 ± 28.7	304.6 ± 19.6
Meibomian gland scores			
• Baseline	8.7 ± 2.4	7.1 ± 2.1	9.2 ± 2.6
• 1 month	7.6 ± 1.8	6.7 ± 2.5	7.2 ± 1.4
• 2 month	8.3 ± 2.0	6.3 ± 2.6	8.2 ± 2.2
• 3 month	8.7 ± 2.0	6.0 ± 2.3	7.3 ± 1.4

**Table 2.** Results of clinical parameters are summarized with the mean and standard deviation demonstrated at weeks 4, 8 and 12 in comparison to baseline.

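### Outcomes are defined as mean changes but no mean change or confidence interval is printed, and zero insert-related events in 10 patients are concluded to show a safe alternative

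*SAP*

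**What the plan says.** The SAP is written as a completed report. Under Main Outcome Measures, "The primary outcome measure was the mean change in corneal surface staining" at weeks 1, 2, 4, 8 and 12, and the secondary measures are also mean changes from baseline. Under Statistical Analysis, "Repeated measures analysis of variance was performed to compare the values at each time point in each group", followed by Bonferroni-corrected comparisons of each visit with baseline; a P "value less than 0.05 was considered statistically significant". No estimate, interval or between-group contrast is specified.

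The table caption describes what is shown: "Results of clinical parameters are summarized with the mean and standard deviation demonstrated at weeks 4, 8 and 12 in comparison to baseline". The Results text adds P values for corneal staining and DEQ-5 only.

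Three conclusions follow:
- Results: "None of the three groups, including the study and two control groups met the primary endpoint".
- Discussion: the topical steroid and insert groups are described as having done alike.
- Conclusion: "The safety profile reported in this study, albeit a small sample size, indicates the dexamethasone intracanalicular insert is a safe alternative option" to topical steroids.

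The protocol's hypotheses (Section 1.2) are between-group: greater symptomatic improvement than pharmacotherapy alone, and non-inferiority to Restasis with Lotemax. No margin is given.

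**The concern.** The quantity named as the outcome is not reported. A reader cannot in general rebuild it, because the SD of a change depends on the correlation between visits, which is not given. With 9 to 11 patients per arm, a P value above 0.05 or a count of zero says little about what the data exclude.

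The stake is greatest for safety. A zero count without an upper limit becomes a positive statement that the insert is safe relative to topical steroids. For efficacy, a statement that the endpoint was not met, or that two groups did alike, leaves the reader unable to tell a demonstrated absence of difference from too little information.

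**Working it through.** **1. Reproducing a printed figure.** In one primary result the SD of change can be recovered. Loteprednol corneal staining is 0.8 ± 1.5 at baseline and 0.0 ± 0.0 at week 8 (SAP, Table 2), so every change equals minus the baseline value and the SD of change is 1.5. With all 22 eyes present:
- SE = 1.5/√22 = 0.320; t = 0.8/0.320 = 2.50 on 21 df; raw P = 0.021.
- Times 3 gives 0.062, against the printed 0.06. Times 5 gives 0.104. With 11 patients, times 3 gives 0.32.

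The match suggests that eyes were the unit and three comparisons were adjusted for. It is only suggestive, since rounding of the printed mean and SD moves the 22-eye, times-3 value between about 0.04 and 0.10.

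**2. Intervals for that result** (change -0.8):

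| Basis | Calculation | 95% interval |
|---|---|---|
| 22 eyes, unadjusted | -0.8 ± 2.080 × 0.320 | -1.47 to -0.13 |
| 22 eyes, Bonferroni ×3 | -0.8 ± 2.601 × 0.320 | -1.63 to +0.03 |
| 11 patients, eyes fully concordant, unadjusted | -0.8 ± 2.228 × 1.5/√11 | -1.81 to +0.21 |

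The observed change is complete clearance, and the intervals run from a large reduction to roughly none, or a small worsening.

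**3. Insert group, week 12 corneal staining.** The mean is 0.7. Baseline is 0.5 in the Results text and 0.6 in Table 2, so the change is +0.2 or +0.1. Inverting the printed P = 0.97 (divided by 3, 20 eyes) gives |t| = 1.014 and:
- change +0.2: about -0.2 to +0.6
- change +0.1: about -0.1 to +0.3

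The width is proportional to a difference that is itself in doubt. At week 8 the text prints 0.5 against 0.5 with P = 0.99, and the same method returns zero width. These intervals should not be relied on.

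**4. The statement that the steroid groups did alike.** As an illustration, take the week 12 DEQ-5 change: insert 10.3 - 14.1 = -3.8; loteprednol 10.2 - 14.4 = -4.2; difference +0.4. The between-visit correlation r must be assumed, with SD of change = √(s0² + s1² - 2·r·s0·s1). By Welch with 10 and 11 patients, the 95% interval is -3.1 to +3.9 at r = 0.7 and -5.4 to +6.2 at r = 0, on a scale of 0 to 22.

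**5. Zero safety counts** (SAP Results; 10 insert patients, 11 loteprednol patients, complete follow-up assumed):
- Insert-related events, 0/10, exact upper limit: 1 - 0.05^(1/10) = 25.9% one-sided; 1 - 0.025^(1/10) = 30.8% two-sided.
- With a true rate of 10% per patient, zero events in 10 would occur with probability 0.9^10 = 35%; with 20%, 0.8^10 = 11%.
- Against topical steroid, the only zero reported for both arms is IOP rise above 10 mmHg. Wilson upper limits are 3.84/(10 + 3.84) = 27.8% and 3.84/(11 + 3.84) = 25.9%, so the Newcombe interval for 0/10 minus 0/11 is about -26 to +28 percentage points. Canalicular and implantation events cannot occur in the loteprednol arm and give no comparison.

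**The case against.** The best reply is that the SAP is already cautious. The Discussion says efficacy remains unclear and calls the study a pilot. The limitations concede the small sample, note that staining was not an entry criterion, and say that "an adequately powered study could lead to meaningful changes in other parameters such as TBUT and Schirmer scores". The Conclusion mentions the small sample in the safety sentence itself and asks for further study. On this view, not meeting the endpoint merely reports the 0.05 rule and does not claim absence of effect.

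Most of this stands for efficacy. A reader might infer that the SAP presents inconclusive efficacy data as a negative finding; its own wording does not support that. A reader might also take the insert group's week 12 interval to run from near-clearance to more than doubling of staining. That requires the 0.5 baseline, the inversion of a near-ceiling adjusted P value and fully concordant eyes; it disappears with the 0.6 baseline. Nor would intervals necessarily show every question as open: if the insert group's DEQ-5 P values were adjusted for five visits rather than three, the implied unadjusted intervals exclude zero, with upper limits of -0.1 to -0.2.

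The reply fails on safety. Acknowledging a small sample does not say what zero events leave open, and the sentence still draws the inference. It also leaves the named outcome unreported and the claim of similarity without an estimate.

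**Conclusion.** The point holds as a reporting defect with one unsupported conclusion. The defined outcome, mean change, is not printed, and neither is any measure of its precision. The safety sentence goes beyond its data: 0/10 does not exclude an insert-related event rate of about 26% to 31%, and the one available comparison with topical steroid leaves a difference of roughly ±26 to 28 percentage points. This does not show that the insert is unsafe; it shows that the question is open.

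For efficacy the defect is narrower. The overall conclusion is suitably guarded, but two summary statements lack estimates, and the one primary interval recoverable without an assumed correlation or P inversion is wide.

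The figures assume complete follow-up, since numbers per visit are not printed, and complete capture of events. Protocol Section 6.2 limits recording to medically relevant events, whereas the SAP says all subject-reported events were recorded. Some opening pages of the SAP were not available, so the absence of intervals is established for its Methods, Results, Discussion, Conclusion and tables.

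**What to change.** 1. Reconcile the insert group's baseline corneal staining between the Results text (0.5) and Table 2 (0.6).
2. In Table 2, print for each arm and visit the n, mean change, SD of change and 95% confidence interval, computed on the average of each patient's two eyes.
3. Add insert-minus-control differences in change with 95% intervals, because the hypotheses in Protocol Section 1.2 are between-group and within-arm intervals would not address them.
4. In the Results, accompany the statement about the primary endpoint with the estimate and interval. In the Discussion, replace the statement of similarity with the between-group estimate and interval.
5. Put the exact upper limit beside each zero safety count.
6. In the Conclusion, replace the safe-alternative claim with: *no insert-related event was seen in 10 patients; a rate up to about 26-31% is not excluded.*

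The cost is one re-run on data already held, a larger table and a few reworded sentences. The safety conclusion becomes less favourable.
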